IWRS	Interactive Web Response System
LA	Left Atrial
MedDRA	Medical Dictionary for Regulatory Activities
NOAEL	No Observed Adverse Effect Level
PAH	Pulmonary Arterial Hypertension
PAP	Pulmonary Artery Pressure
PH	Pulmonary Hypertension
PI	Primary Investigator
PK	Pharmacokinetic
PVR	Pulmonary Vascular Resistance
Q4W	Every Four Weeks
QTc	QT Interval Corrected for Heart Rate
QTcF	QT Interval Corrected for Heart Rate Using Fridericia's Method
REMS	Risk Evaluation Mediation Strategy
RHC	Right Heart Catheterization
RVSP	Right Ventricular Systolic Pressure
SAE	Serious Adverse Event
SAP	Statistical Analysis Plan
$t_{1/2}$	Terminal Elimination Half-Life
T_{max}	Time to maximum serum concentration
TMF	Trial Master File
ULN	Upper Limit of Normal
WHO	World Health Organization

1. INTRODUCTION

Pulmonary arterial hypertension (PAH) is a rare, progressive, life-threatening disease caused by obliteration of the small, peripheral pulmonary arteries by endothelial and smooth muscle cell proliferation and in-situ thrombosis. Progressive obstruction of the distal arteries leads to increasing pulmonary vascular resistance (PVR), pulmonary artery pressure, right heart failure, severe debilitation and, eventually death.¹ Of the 5 categories of pulmonary hypertension described at the 5th World Symposium on Pulmonary Hypertension held in Nice, France, in 2013, PAH is classified as Group 1 indicating that it is a primary vascular disease and not caused by post-capillary pressure backup from left heart disease, parenchymal lung disease or pre-capillary chronic thromboembolic disease. PAH most commonly has no clear cause or association (idiopathic) but can be genetically based, drug or toxin-induced or associated with collagen vascular disease, congenital heart disease, human immunodeficiency virus (HIV), portal hypertension or schistosomiasis.² While an imbalance of vasoconstrictive and vasorelaxant factors is felt to be an underlying cause of progressive disease in all forms of PAH, the end results in all cases include pulmonary arteriolar constriction, in-situ thrombosis and pulmonary vascular remodeling.³

An array of pharmacotherapeutic approaches for PAH have been developed over the past two decades and provide dramatic improvement in PAH-associated symptoms and quality of life.⁴ Most of these molecules have been approved based on short-term (12 to 24 week) studies demonstrating improvement in exercise tolerance primarily demonstrated by increasing distance on the 6MWT. More recently, reduction of disease progression with the mixed endothelin receptor antagonist macitentan and the selective prostacyclin receptor agonist selexipag has been reported.^{5,6}

Based on data obtained over three decades ago by the US National Institutes of Health, patients with untreated PAH have a median survival of 2.8 years. To date, no single therapy, with the possible exception of intravenous epoprostenol,⁷ has been clearly associated with increased survival. This may be due to the small sample sizes and limited follow-up of individual studies. Indeed, there are clear trends in improved survival. Meta-analysis combining studies averaging 14.8 weeks of follow-up suggest that current treatment modalities may have had a substantial impact on survival though this has yet to be clearly documented in a long-term outcome study.⁸

Current pharmacologic treatment of PAH leverages imbalances in vasoconstrictive/vasodilatory pathways including the endothelin, nitric oxide and prostacyclin systems. Based on some studies showing improvement in clinical outcomes, there is an increasing use of initial combined therapy.⁹ The actual sequencing of treatment additions is not entirely clear though prostanoids are not usually prescribed as initial therapy.⁹ Treatment options currently include prostanoids, synthetic analogues of prostacyclin, and the prostacyclin receptor agonist, selexipag, which have vasodilatory as well as antiproliferative effects. Vasodilator drugs work by increasing cyclic guanosine monophosphate (cGMP) downstream and include the phosphodiesterase-5 inhibitors (e.g. sildenafil and tadalafil), which reduce cGMP degradation and the soluble guanylate cyclase agonists (e.g. riociguat) which both stimulate soluble guanylyl cyclase production and sensitize cGMP to nitric oxide.

Endothelin-1 (ET-1) is a 21 amino acid endothelial cell-derived polypeptide and one of the most potent vasoconstrictors known. Stimulation of the endothelin type A and B

g-protein-coupled receptors (ET_A and ET_B) causes vascular smooth muscle contraction and stimulates smooth muscle proliferation. Thus, blockade of ET-1 may have both vasodilatory and antiproliferative effects which could blunt or even reverse pulmonary vascular remodeling. While principally found in endothelial cells, a range of other cell types have also been shown to express endothelin including cardiac myocytes, lung epithelium, glomerular kidney cells, mesangial cell, leukocytes, and macrophages.

1.1. Overview

GMA301 is an anti-endothelin receptor type A humanized monoclonal antibody. The molecular weight is around 148kDa.

1.2. Summary of Nonclinical Pharmacology

The completed nonclinical studies of GMA301 include in vitro potency testing, in vivo efficacy study in cynomolgus monkeys, single and repeat doses pharmacokinetics (PK) and toxicity studies also in cynomolgus monkeys.

An in vitro study of the biological activity of GMA301 was conducted in Chinese hamster ovary (CHO) cells with rats, monkey and human ET_A expressed. Ambrisentan was used as a positive control. Results showed that GMA301 has a similar IC50 value on monkey and human ET_A (67.55 and 57.50 nM) but does not bind to rat ET_A, which proved that GMA301 has a species specificity in ET_A binding. The positive control,

ambrisentan, showed similar inhibitory potency in 3 cell lines with IC50 of 1.61, 2.84, and 8.07 nM on rat, monkey, and human ET_A.¹⁸

In an efficacy study of GMA301 administered intravenously twice per week for 6 weeks in a monocrotaline-induced PAH model in cynomolgus monkeys, right ventricular systolic pressure (RVSP) of GMA301 decreased by 13.6%, 45.7%, and 54.0% in 1.5, 5, and 15 mg/kg dose groups (p<0.01 in 5 and 15 mg/kg groups compared to the model group) and Fulton's index (weight of right ventricular/(weight of left ventricular plus weight of interventricular septum)*100%) decreased by 31% in the 5 mg/kg group.¹⁸

The results indicated that the efficacy of 5 mg/kg GMA301 was similar to ambrisentan. The dose of ambrisentan used in this study is 1 mg/kg, which is administrated once a day for 6 weeks by oral gavage.

1.3. Summary of Safety Pharmacology

Although mice are not relevant species to GMA301, a single dose toxicity study was still conducted. Both GMA301 injection and placebo result in some death after IV injection at a very high dosage (equal to 6.9-gram GMA301 injected in a 60 kg human). The cause of death may need further study, however, according to International Council for Harmonisation (ICH) S6, "Toxicity studies in non-relevant species may be misleading and are discouraged". Therefore, the results of acute toxicity study in mice may not be relevant for the preclinical safety evaluation of GMA301.

The preclinical toxicity studies included single and repeat doses of GMA301 were conducted in cynomolgus monkeys.

In single dose toxicity study, cynomolgus monkeys were administrated at 75, 250, and 750 mg/kg, No GMA301-related changes were noted in clinical observations, body weight, hematology and clinical chemistry tests. The no observed adverse effect level (NOAEL) was 750 mg/kg.

In a multiple dose toxicity study in cynomolgus monkeys, GMA301 was administrated at 25, 75, and 250 mg/kg twice weekly for 4 weeks and 25, 75, and 250 mg/kg once weekly for 13 weeks followed by a six-week recovery period. No changes were noted in clinical observations, body weight, body temperature, hematology and clinical chemistry. No GMA301-related histopathology abnormality was found.¹⁸

1.4. Summary of Nonclinical Pharmacokinetics

A total of 24 naive cynomolgus monkeys (3 males and 3 females in each group) were used in a single and repeat dose PK study. In the single dose study, GMA301 was injected at 5, 15, 50 mg/kg and in the multiple dose study, injected at 15 mg/kg once weekly for 4 consecutive weeks. Blood was collected at different timepoints and PK parameters were calculated. GMA301 showed a long half-life of approximately 244.74, 173.15, and 173.41 hours in 5, 15, and 50 mg/kg group after single dose injection. After a total of 4 injections, the AUC of the last dose of 15 mg/kg was 1.96 times higher than that of the first dose, at 47.96 and 24.50 h·mg/mL, respectively.¹⁸

Table 1: Pharmacokinetics Parameters of GMA301 in monkeys

Group	Dose (mg/kg)	t_{1/2} (h)	C_{max} (μ g/mL)	AUC_{inf} (h·mg/mL)	
Single dose	5	244.74±30.29	98.22±16.81	16.10±2.31	
	15	173.15±63.14	317.57±38.19	40.26±15.21	
	50	173.41±24.65	1014.96±73.63	137.50±23.34	
Group	Dose	t_{1/2} (h)	C_{max} (μ g/mL)	AUC_(0-168 h) (h·mg/mL)	F
Repeat dose*	15mg/kg-first dose	182.81±46.82	326.27±41.49	24.50±2.75	
	15mg/kg-last dose	263.54±38.67	481.76±59.05	47.96±3.59	1.96

*: 15 mg/kg once per week for 4 weeks. F=AUC_{last}/AUC_{first}; t_{1/2}=Terminal Elimination Half Life; C_{max}=Maximum Observed Serum Concentration

1.5. Summary of Clinical Experience

1.5.1. Safety

A single-center, double-blind, placebo-controlled, dose escalation study to assess the safety, tolerability, and PK of GMA301 in healthy subjects was performed in Australia. Four sequential dosing cohorts, each with 6 subjects receiving GMA301 and 2 subjects receiving placebo (total of 32 subjects), were given increasing single doses of GMA301. The administered doses were 75, 200, 500, and 1000 mg, or matching placebo. The most frequent Treatment Emergent Adverse Events (TEAEs) across the 4 groups were headache (39.4%), nausea (12.1%) and pharyngitis (12.1%). All of these TEAEs were well tolerated without further medical intervention needed.

1.5.2. Pharmacokinetics

Pharmacokinetic results were obtained from the same study that was performed in Australia. All individuals in the study exhibited quantifiable plasma GMA301 concentrations at the first timepoint of 4 hours. Most individuals appeared to exhibit mono-exponential pharmacokinetics, with a slow decline in plasma concentrations after attainment of Maximum Observed Serum Concentration (C_{max}). Terminal half-life was long with average values ranging from 503.75 hours to 565.63 hours.

Other pharmacokinetic values of GMA301 refer to clinical study report of GMA301 Australia study.¹⁹

1.6. Study Rationale

The selection of GMA301 doses and dosing frequency was based on the available clinical safety, tolerability and PK data obtained from healthy human subjects¹⁹. The dose level of 1000 mg GMA301 observed in the previous Phase Ia study has been proven safe for human subjects. Based on that, we believe that GMA301 dosed at 300, 600, and 1000 mg every 4 weeks (Q4W) should be safe for human subjects.

The principal aim of this study is to obtain safety and tolerability data when GMA301 is administered as multiple doses in subjects with PAH. This information, together with the PK data, will help establish the doses and dosing regimen for future studies. The efficacy parameters of GMA301 will also be investigated.

1.7. Benefit-risk Assessment

Subjects enrolled in this study will receive no known benefit from the study drug. Subjects will undergo additional testing (e.g. right heart catheterization [RHC], echocardiography, 6MWT and biomarkers) that may help their practitioner better characterize their disease. The risks of participation are primarily those associated with adverse reactions to the investigational medicinal product (IMP). In addition, there may also be some discomfort or morbidity from the RHC and collection of blood samples and other study procedures.

More information about the known and expected benefits, risks, and reasonably anticipated adverse events (AEs) associated with GMA301 may be found in the Investigator's Brochure ¹⁸.

2. OBJECTIVES AND ENDPOINTS

2.1. Objectives

2.1.1. Primary Objective

- To assess the safety and tolerability of GMA301 following repeated intravenous (IV) dosing in subjects with World Health Organization (WHO) Group-1 PAH

2.1.2. Secondary Objectives

- To determine the PK and dose/exposure-response relationships of GMA301
- To evaluate the effects of GMA301 on hemodynamics
- To evaluate the effects of GMA301 on exercise tolerance
- To evaluate the effects of GMA301 on relevant PAH biomarkers

2.1.3. Exploratory Objectives

- To evaluate the effects of GMA301 on REVEAL 2.0 risk score (See [Appendix 7](#))

2.2. Endpoints

2.2.1. Primary Endpoints

The incidence of TEAEs in subjects assigned to GMA301 compared with those assigned to placebo

2.2.2. Secondary Endpoints

- Pharmacokinetics
 - Area under the serum concentration- time curve from time zero to the last measurable concentration (AUC_{0-t})
 - Area under the serum concentration- time curve over a dosing interval (AUC_{0- τ})
 - Observed maximum serum concentration (C_{max})
 - Area under the serum concentration-time curve from time zero to infinity (AUC_{0-inf})
 - Time to maximum serum concentration (T_{max})
 - Terminal elimination half-life (t_{1/2})
 - Volume of distribution
 - Trough concentration
 - Clearance
 - Accumulation ratio
- Comparison of GMA301 treatment effect at Week 12 versus baseline regarding the hemodynamic parameters based on RHC. Parameters include but are not limited to:
 - Pulmonary vascular resistance (PVR)
 - Mean pulmonary arterial pressure (mPAP)
 - Cardiac index
- Comparing the following treatment effect metrics:
 - 6MWT distance (Week 12 versus Screening)
 - NT-pro BNP level (Weeks 4, 8, and 12 versus baseline)
 - WHO functional class (Weeks 8 and 12 versus baseline)

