- Any clinically relevant sign or symptom (eg, Class IV heart failure) that, in the opinion of the Investigator (or designee), warrants subject withdrawal.

Subject who didn't get IMP treatment within protocol defined timeline with any reason can get back to the IMP treatment with investigator or SRC's evaluation and agreement.

All the discontinuation must be documented accordingly. If a subject is withdrawn, the Sponsor will be notified in 24 hours and the date and reason(s) for the withdrawal will be documented in electronic Case Report Form (eCRF). In this case, efforts in any ways must be made to complete the follow up assessments. ([Appendix 6](#)). Other medical procedures may be performed at the Investigator's discretion. The Investigator may also request subjects to return for additional Follow-up visits. All AEs will be followed until recovery or stabilization.

Cohort discontinuation and study termination

The SRC will discontinue or stop the cohort or even the study in case of :

- Two cases discontinuations in a cohort due to events related to the study drug under the diagnosis of the investigators;
- Single case with severe allergic event related to study drug;
- Known and expected AEs are with increased frequency, severity and or long lasting.

The sponsor can terminate the study with notification to the investigators.

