8.3. Analysis Populations

8.3.1. Pharmacokinetic Population

The PK population will include all subjects who received at least 1 dose of study drug (GMA301) and have at least 1 evaluable PK data.

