8.5. Pharmacokinetic Analyses

Non-compartmental PK analysis will be performed on individual serum concentration data, using commercial software such as Phoenix® WinNonlin®. Serum concentrations of GMA301 and PK parameters will be listed and summarized using descriptive statistics. Individual and mean GMA301 concentration-time profiles will also be presented graphically.

In the study, where data are available, GMA301 dose proportionality will be examined across dose groups. The PK parameters will be analyzed for dose proportionality using a power model approach or analysis of variance (ANOVA) model as appropriate.

Other parameters may be added as appropriate. Final PK parameters reported will be detailed in the SAP.

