- d. Tests can also be done on the last day of Week 11. If a subject discontinues the visit in advance, it would be better to ask the subject to complete the Week 12 examinations.
- e. Serology tests refer to Hepatitis B surface antigen, Hepatitis C antibody, and Human Immunodeficiency Virus antibodies ([Appendix 2](#)).
- f. Women of childbearing potential will perform pregnancy test in serum at Screening and in urine at randomization and Weeks 4, 8, and 12.
- g. FSH test will be performed at the same time with serum pregnancy test at Screening.
- h. ADA will be collected at: Week 0 (pre-dose of the 1st dose), Week 2, Week 4 (prior to 2nd dose), Week 8 (prior to 3rd dose), Week 12 and Week 18 (end of follow-up).

Pharmacokinetics sampling:

Pharmacokinetics serum samples will be obtained for PK assessments at the following timepoints (\pm Time window):

[figure not shown]
Dose 1st: predose, 4 (\pm 15 min), 8 (\pm 30 min), 24 (\pm 120 min), 72 (\pm 240 min), 168 (Day 8; \pm 480 min), 336 (Day 15; \pm 1 day), 504 (Day 22; \pm 1 day), and 672 (Day 29; \pm 1 day) hours post dose.

Dose 3rd: predose, 4 (\pm 15 min), 8 (\pm 30 min), 24 (\pm 120 min), 72 (\pm 240 min), 168 (Day 8; \pm 480 min), 336 (Day 15; \pm 1 Day), 504 (Day 22; \pm 1 day), 672 (Day 29; \pm 1 day), 1008 (Day 43; \pm 2 day), 1344 (Day 57; \pm 3 day), 1680 (Day 71; \pm 3 day) hours postdose.

The samples of the 672h post 1st dose will be collected before the 2nd dose.

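### Does Section 8.5 have to state which dose's profile gives each pharmacokinetic parameter?

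*Combined protocol and SAP*

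**What the plan says.** Section 2.2.2 gives generic definitions. Two of them are "Area under the serum concentration- time curve from time zero to the last measurable concentration (AUC_{0-t" and "Area under the serum concentration-time curve from time zero to infinity (AUC_{0-inf". AUC0-tau, volume, clearance and accumulation ratio are also listed, and none is tied to a dose.

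Section 8.5 specifies non-compartmental analysis, descriptive summaries, and dose proportionality by power model or ANOVA. It then adds: "Final PK parameters reported will be detailed in the SAP". The documents supplied contain no SAP text on PK derivations.

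Appendix 6 samples two profiles:

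- Dose 1: nine samples, predose to 672 h. "The samples of the 672h post 1st dose will be collected before the 2nd dose".
- Dose 3: twelve samples, predose to 1680 h.

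On who contributes, Section 8.3.1 says "The PK population will include all subjects who received at least 1 dose of study drug (GMA301" and also requires at least one evaluable PK result. Section 3.6 says that subjects not treated "within protocol defined timeline with any reason can get back to the IMP treatment" if the investigator or SRC agrees.

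The only accumulation formula in the documents is for the monkey study, under Table 1 in Section 1.4: "F=AUC_{last}/AUC_{first".

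**The concern.** The two profiles are not interchangeable. The first is cut off by the second dose after one dosing interval. The other runs for 2.5 intervals and starts with drug left from two earlier doses. Because the half-life is close to the dosing interval, a sizeable part of dose 1 exposure falls after 672 h, and carry-over into dose 3 is substantial. One parameter name can therefore stand for different quantities:

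- AUC0-t could cover 672 h or 1680 h.
- AUC0-inf after dose 3 includes carry-over unless it is removed.
- Clearance and volume inherit whichever AUC is used.
- The accumulation ratio depends on which areas are divided.

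Subjects with one dose, or with a missed dose, have no dose 3 profile or a different carry-over, and no rule covers them.

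PK is the first secondary endpoint, and Section 1.6 says it will inform later dose and regimen choices. Tables that mixed readings, or a choice made after seeing the data, could mislead.

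**Working it through.** **The plan's own figure.** Table 1 gives monkey AUC over 0-168 h of 24.50 (first dose) and 47.96 (last dose): 47.96/24.50 = 1.96, as stated. Superposition over four weekly doses with the first-dose half-life of 182.81 h gives r = exp(-168 × ln2/182.81) = 0.529 and (1 - r⁴)/(1 - r) = 1.96. Simple superposition reproduces the sponsor's equal-interval ratio.

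**Inputs for this trial.** Section 1.5.2: "Terminal half-life was long with average values ranging from 503.75 hours to 565.63 hours", with most individuals mono-exponential. Dosing interval 672 h, three doses (Section 3.1). Last samples at 672 h and 1680 h (Appendix 6). Assumption: healthy-subject half-lives and linear kinetics apply in PAH.

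**Formulas.** k = ln2/t½; r = exp(-672k), which is 0.397 at 503.75 h and 0.439 at 565.63 h. After dose 3, superposition multiplies the single-dose curve by 1 + r + r². Areas below are in units of Dose/CL.

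| Area | Formula | 503.75 h | 565.63 h |
|---|---|---|---|
| Dose 1, AUC0-t = AUC0-tau (672 h) | 1 - r | 0.603 | 0.561 |
| Dose 1, AUC0-inf | 1 | 1 | 1 |
| Dose 3, AUC0-tau | 1 - r³ | 0.938 | 0.915 |
| Dose 3, AUC0-t (1680 h) | (1 + r + r²)(1 - exp(-1680k)) | 1.400 | 1.423 |
| Dose 3, AUC0-inf, carry-over left in | 1 + r + r² | 1.554 | 1.632 |
| Dose 3, AUC0-inf less Cpredose/λz | (1 + r + r²) - (r + r²) | 1 | 1 |

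**Clearance as a multiple of truth (volume follows as CL/λz).**
- Dose/AUC0-inf, dose 1: 1.00, with 40-44% of the area extrapolated.
- Dose/AUC0-tau, dose 3: 1/0.938 = 1.07 to 1/0.915 = 1.09.
- Dose/AUC0-inf, dose 3, carry-over left in: 1/1.554 = 0.64 to 1/1.632 = 0.61.
- The same with carry-over subtracted: 1.00.

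**Accumulation, dose 3 over dose 1.**
- AUC0-tau: 1.55 to 1.63.
- AUC0-t: 1.400/0.603 = 2.32 to 1.423/0.561 = 2.54. This divides 1680 h by 672 h.

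**Missed Week 4 dose, Week 8 given.** The carry-over factor falls to 1 + r² = 1.157 to 1.193. Dose/AUC0-tau becomes 1/((1 + r²)(1 - r)) = 1.43 to 1.49 times truth. One such subject in nine shifts the cohort geometric mean by (1.432/1.067)^(1/9) = 1.033 to (1.494/1.092)^(1/9) = 1.035.

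**Dose proportionality.** With one half-life across cohorts, changing the source profile multiplies every cohort by the same factor and leaves the power-model slope unchanged. Suppose instead that the two extreme half-lives fell at 300 and 1000 mg. Moving from dose 1 AUC0-inf to dose 3 AUC0-tau would then change the slope by ln(0.915/0.938)/ln(1000/300), about -0.02. Moving from dose 1 AUC0-t to dose 3 AUC0-t would change it by ln(2.537/2.320)/ln(1000/300), about 0.07.

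**The case for a change.** The strongest reply is that Section 8.5 promises that the SAP will give the final parameters, which is not the same as derivation rules. The sponsor also specified dose, interval and ratio for the monkeys but not for the subjects of this trial. Convention does not fix the AUC0-t window, and nothing in the text forbids an uncorrected dose 3 AUC0-inf.

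All of that is accurate as a reading of the text. It shows that a rule is unwritten. It does not show that a wrong result is likely:

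- The window of AUC0-t depends on the profile by definition. Appendix 6 keeps the two profiles apart, and nothing suggests pooling them.
- AUC0-tau is listed separately, and the sponsor's own precedent is an equal-interval ratio, so the default for accumulation is clear.
- Using dose 3 AUC0-inf with carry-over left in to obtain clearance is an error rather than a competing convention, and the documents do not propose it.
- Concentrations and parameters are listed by subject (Sections 8.1 and 8.5), so any derivation can be recomputed.

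Writing rules in now has a drawback too. Subtracting the predose term requires linear, time-invariant elimination. Table 1 shows monkey half-life rising from 182.81 h after the first dose to 263.54 h after the last. A bias figure of 7 to 9% for Dose/AUC0-tau would rest on healthy-subject data.

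**Conclusion.** No change to the plan is called for. This is a gap that a pharmacokineticist fills in the ordinary course of a non-compartmental analysis. Areas are labelled by dose and window, accumulation is taken over equal intervals, and carry-over is kept out of clearance and volume. Incomplete or off-schedule profiles are flagged.

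Handled that way, the choice that remains for clearance and volume is worth 7 to 9%, and an occasional missed Week 4 dose 3 to 4% on a cohort geometric mean. The bigger differences (1.55- to 1.63-fold for uncorrected AUC0-inf, 2.32- to 2.54-fold for AUC0-t across doses) come from comparing unlike quantities. No hypothesis test depends on the choice, Section 8.9 plans no interim analysis, and the review items that Section 3.5 names for dose escalation are safety data. A line per parameter in the SAP would be a convenience, and the SAP may already have one.

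The figures assume that the healthy-subject half-lives of 503.75 to 565.63 h carry over to PAH, linear mono-exponential kinetics, and measurable concentrations through 1680 h. Marked non-linearity or antibody-driven clearance would change them, but a derivation rule fixed in advance from healthy-subject data would not resolve that.

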8. SAMPLE SIZE AND DATA ANALYSIS

8.1. General Analysis

Statistical analyses will be descriptive only, with no hypothesis testing. Analyses will be performed in SAS®. Summary tables will present results for each of the three GMA301 doses. Descriptive statistics including the number (n), the arithmetic mean (Mean), standard deviation (SD), median, the minimum value (Min), and the maximum value (Max) will be presented for continuous variables, and the number of subjects (n) and the percentage (%) will be presented for categorical and ordinal variables. All study data will also be presented in by subject data listings. The details of the statistical analysis will be described in the Statistical Analysis Plan (SAP).

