8.7. Efficacy Analyses

The Safety Population will be used for efficacy analyses.

Efficacy endpoints including hemodynamic parameters, 6-minute walk distance, NT-proBNP levels, WHO functional class, and their change from baseline will be listed and summarized by treatment group using descriptive statistics as appropriate at each collection timepoint.

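### Efficacy endpoints are worded as Week 12 versus baseline and the protocol plans no GMA301-versus-placebo estimate or interval, although 9 of 36 subjects are randomized to placebo

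*Combined protocol and SAP*

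**What the plan says.** - Section 2.2.2 words the RHC endpoint as "Comparison of GMA301 treatment effect at Week 12 versus baseline regarding the hemodynamic parameters based on RHC". The 6MWT, NT-proBNP and WHO functional class metrics in the same section are also called treatment effect metrics and name only time points. The synopsis uses the same wording.
- Section 2.2.1 does name the comparator for safety: "The incidence of TEAEs in subjects assigned to GMA301 compared with those assigned to placebo".
- Section 8.7 says that efficacy values and their changes from baseline will be listed and "summarized by treatment group using descriptive statistics as appropriate at each collection timepoint".
- Section 8.1 says "Statistical analyses will be descriptive only, with no hypothesis testing" and "Summary tables will present results for each of the three GMA301 doses". For continuous variables it lists n, arithmetic mean, SD, median, minimum and maximum. It defers further detail to a SAP; the supplied document contains no SAP text beyond section 8.
- Sections 5.3 and 8.2 randomize 9 subjects to GMA301 and 3 to placebo in each of three cohorts.
- Section 8 contains no between-arm efficacy difference, confidence interval, baseline adjustment, log-scale efficacy summary or rule for pooling placebo over cohorts.

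**The concern.** Section 2.1.2 sets out to evaluate the effects of GMA301 on hemodynamics, exercise tolerance and biomarkers. A change from baseline within the treated arm is not an effect of the drug unless nothing else would have changed, and the protocol leaves room for other change:

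- **Selection.** The entry rules in section 4.1 use the outcome variables themselves: mPAP of at least 25 mmHg, PVR above 3 Wood units, 6MWT between 150 and 450 m. Some regression to the mean is expected without any drug.
- **Time.** Section 4.1 lets an RHC from up to 3 months before Screening serve as baseline, so the interval over which change is measured differs between subjects.
- **Practice.** This could affect the 6MWT only. The schedule in Appendix 6 shows one test at Screening and one at Week 12.

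The randomized placebo arm deals with all three in expectation, but only if the comparison is made. Without a planned contrast, readers will subtract columns by eye, with no uncertainty attached, and can choose afterwards between 3 own-cohort and 9 pooled placebo subjects.

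**Working it through.** **The plan's own figure.** 3 × (9 + 3) = 36, of whom 27 receive GMA301 and 9 placebo. This reproduces as a headcount. Section 8.2 gives no power calculation, effect size or SD, so the results below are in SD units or rest on stated assumptions.

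**Time span.** Taking 3 months as 91 days and Screening as up to 28 days, a baseline RHC can precede dose 1 by 91 + 28 = 119 days and Week 12 by 119 + 84 = 203 days. Done at dosing, the span is about 84 days.

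**Selection with no drug effect.** Expected change = (population mean − mean after truncation at the entry limits) × (1 − retest correlation). Population values are assumed normal; the correlation is assumed to be 0.6 to 0.9.

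- mPAP (mean/SD from 30/10 to 50/14 mmHg): −0.1 to −2.0 mmHg. At 45/12 and correlation 0.8: −0.25 mmHg.
- PVR (6/3 to 10/5 Wood units): about −0.1 to −0.35 units, or −1% to −5%.
- 6MWT (350/90 to 450/90 m): +2 to +29 m. At 400/90 and correlation 0.8: +8.5 m.

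All three are in the direction of apparent benefit.

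**Precision, in SDs of change.** SE = √(1/n1 + 1/n0), or 1/√n within an arm; half-width = t(0.975) × SE.

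| Contrast | SE | df | 95% half-width |
|---|---|---|---|
| Within one dose, n = 9 | 0.33 | 8 | 0.77 |
| One dose v own-cohort placebo, 9 v 3 | 0.67 | 10 | 1.49 |
| One dose v pooled placebo, 9 v 9 | 0.47 | 16 | 1.00 |
| All doses v pooled placebo, 27 v 9 | 0.38 | 34 | 0.78 |

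A single four-group model has 36 − 4 = 32 df, which trims the 9 v 9 half-width slightly: 2.04 × 0.471 = 0.96.

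**Baseline adjustment.** The large-sample SE ratio of the adjusted difference to the change-score difference is √((1 + r)/2): 0.866, 0.922 and 0.975 at r = 0.5, 0.7 and 0.9. At this sample size the lost degree of freedom and chance imbalance matter. Simulated interval widths, adjusted relative to unadjusted:

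- four groups of 9: 0.88, 0.94, 0.99 (12%, 6% and 1% narrower);
- 9 v 3: 0.93, 0.99, 1.04 (7% and 1% narrower, then 4% wider).

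**NT-proBNP scale.** Assume a true ratio of 0.75, lognormal values with between-subject log SD 1.0 to 1.2, log-change SD s of 0.5 to 0.7, and 9 v 9. The probability that the estimate points the wrong way is:

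- difference in arithmetic mean change: about 20–29% (simulation);
- difference in median change: about 18–26% (simulation);
- geometric mean ratio: Φ(ln 0.75 / (s√(2/9))) = Φ(−1.22) = 11% at s = 0.5 and Φ(−0.87) = 19% at s = 0.7; simulation gives 11–20%.

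**The case against.** **Placebo would be shown anyway.** Summaries in section 8.7 are by treatment group, and placebo is a randomized treatment, so its change would ordinarily appear beside the active groups. This stands in large part. A reader might infer that the plan counts time, practice and selection effects as drug effect; the documents do not say so. What remains is the endpoint label, the fact that section 8.1 names only the dose groups, and the lack of a difference, an interval or a pooling rule.

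**The SAP may supply the rest.** Section 8.1 defers detail, and its list of statistics is introduced as non-exhaustive. So one can say only that these items are absent from the protocol. The endpoint wording, however, is protocol text, and a SAP should not have to redefine it.

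**The study is descriptive, small and mainly about safety.** True, but an estimate with an interval is not a hypothesis test, and section 8.5 already allows a power model or ANOVA for PK. Small groups make displayed uncertainty more useful, not less.

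**Precision.** A reader might infer that precision is being thrown away for nothing. That is too strong. The placebo contrast has a larger SE than within-arm change (0.47 v 0.33 SD), and the adjustment gain is modest, vanishing or reversing with 3 own-cohort placebos.

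**Practice and skewness.** Practice does not apply to RHC measures. Section 7.3.3 refers 6MWT conduct to a site manual, so a practice walk cannot be ruled out. The median and by-subject listings are planned, so one extreme NT-proBNP value would be visible; under the assumptions above the median still performs worse than the log scale.

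**Conclusion.** The point holds as a cheap improvement. The protocol calls a Week 12 versus baseline contrast a treatment effect, gives no efficacy estimate or interval against its randomized placebo arm, and is inconsistent between sections 8.1 and 8.7 on which groups are tabulated. The main gain from correcting this is a contrast protected by randomization with its uncertainty visible: about ±1.0 SD of change for one dose and ±0.78 SD for all doses combined, both against pooled placebo. Better precision is secondary and depends on the assumed correlation.

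The size and direction of any time effect cannot be derived from the documents. Selection effects rest on assumed distributions; they are probably small for mPAP and PVR and could be larger for the 6MWT. The NT-proBNP comparison also rests wholly on assumed inputs.

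**What to change.** 1. In section 2.2.2 and the synopsis, define the hemodynamic endpoint as change from baseline to Week 12, GMA301 versus placebo. Name the comparator for the 6MWT, NT-proBNP and WHO class metrics in the same way. In section 8.1 name a placebo column, so that it agrees with section 8.7.
2. In section 8.7 add, for continuous endpoints and as estimation only, the difference from placebo pooled over cohorts for each dose and for all doses combined. Give 95% confidence intervals from one linear model per endpoint with the baseline value as covariate. Show placebo by cohort.
3. Analyse NT-proBNP and PVR as log ratios to baseline and report geometric mean ratios. Keep the planned mean and median tables.

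The cost is a wording change and one model per endpoint, with no new data or visits. The downsides are wide intervals, a larger SE than within-arm change, and an assumption that placebo response does not drift across sequential cohorts; with 3 placebo subjects per cohort, the by-cohort display can only flag gross drift.
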